The groups will be compared using a Cox-regression models. The proportionality assumptions will be tested using Schoefeld test and plots. If the PH assumption is violated, we will allow time-varying effects by including covariate $\times$ log(time) interactions or using time-split intervals. Use of competing-risk models will be employed where relevant and feasible. The statistical analysis will be captured in a statistical report with aggregated data in tables. In the primary analyses, overlapping events will be attributed to the drug to which the patient has been exposed for the longest duration.

P-values may be reported when relevant for descriptive purposes and will not be adjusted for multiple testing; they are presented as descriptive statistics only, and no hypotheses are being tested.

A sensitivity analysis will be conducted requiring only one use of a drug to fulfil the inclusion criteria.

To evaluate the robustness of the method applied to handle overlapping events in the primary analysis, multiple sensitivity analyses will be performed, in which overlapping events will alternatively be assigned to (a) the most recently administered drug, (b) attributed to both drugs, or (c) excluded by censoring the patient at the time of the event. These results will be presented separately.

Furthermore, a sensitivity analyses will be conducted reporting incidence rates for the years 1995-2001, 2002-2008, 2009-2015, and 2016-2022.

As a sensitivity analyses, a cox regression model with inverse Probability Treatment Weighting will be conducted.

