### Treatment series

Treatment series are defined as periods of time in which a patient is considered on active treatment. The allowable gap between administrations of the same drug is 150 days to aggregate the treatment series. If the gap exceeds 150 days, patients are considered to have initiated a new treatment series. The allowable gap is based on the common gap of 90 days between each filled prescription, with an additional extension of 60 days to mirror the design of ORALSURV, which allowed for up to 2 months of discontinuation for safety issues.

The duration of active therapy following the last filled prescription or administration is set at 120 days, reflecting the standard 90-day prescription interval plus an additional 30 days, as outlined by Fleischmann et al. . Each treatment series is considered separately, as concomitant therapies were allowed in the ORALSURV study design.

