### Follow-up and exposure and censoring

Patients are followed from the index date until the earliest occurrence of one of the following: the event of interest, the study closing date (30 December 2022), initiation of a

biological therapy or JAK inhibitor, death, the development of a condition that would qualify for one of the treatments of interest (Table 1), or migration.

When using treatment series, exposure time is calculated and cumulated based on the specific therapy received. Except for the event of interest, any of the previously mentioned cases will result in censoring.

Additional analyses will be conducted on an intention-to-treat basis.

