## Events

During the treatment series, an adverse event can be adjudicated to the ongoing treatment. In the intention-to-treatment (ITT) study design, the event can be adjudicated to the treatment initiated at the index date.

If a patient is receiving overlapping treatments, any adverse event occurring during both therapies will be adjudicated to the therapy the patient has been on for the longest duration. Such events are referred to as overlapping events.

In the primary analyses, for overlapping events, the event is assigned to the drug the patient has been on the longest.

Multiple sensitivity analyses will be conducted to address overlapping events:

- The event is assigned to the most recent drug.
- The event is attributed to both drugs.
- The event is attributed to neither drug and the patient is censored.

Serious infections are defined as those requiring hospital admission for more than one day (Table V), and infections with HIV, hepatitis B or C, tuberculosis, or infections resulting in death.

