To evaluate the robustness of the method applied to handle overlapping events in the primary analysis, multiple sensitivity analyses will be performed, in which overlapping events will alternatively be assigned to (a) the most recently administered drug, (b) attributed to both drugs, or (c) excluded by censoring the patient at the time of the event. These results will be presented separately.

Furthermore, a sensitivity analyses will be conducted reporting incidence rates for the years 1995-2001, 2002-2008, 2009-2015, and 2016-2022.

As a sensitivity analyses, a cox regression model with inverse Probability Treatment Weighting will be conducted.

Analyses will be conducted using SAS 9.4, Python v3.11.5, and R v4.4.1

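### Overlap sensitivity analysis (c) censors patients because of the event, so it can count no event during combined therapy while the event-free combined time appears to stay in the denominator

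*Protocol*

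**What the plan says.** Section 8.7, *Events*, calls an event overlapping when it occurs while two therapies are running. In the primary analysis "any adverse event occurring during both therapies will be adjudicated to the therapy the patient has been on for the longest duration". Three alternatives follow: assign the event to the most recent drug, assign it to both drugs, or, third, "The event is attributed to neither drug and the patient is censored". The *Tertiary statistical analysis* text in the same section repeats the third option as "c) excluded by censoring the patient at the time of the event", and the Abstract has the same words. The stated purpose of the three alternatives is to check how robust the primary handling of overlapping events is.

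On person-time, *Follow-up and exposure and censoring* says "When using treatment series, exposure time is calculated and cumulated based on the specific therapy received". *Treatment series* says "Each treatment series is considered separately, as concomitant therapies were allowed in the ORALSURV study design", and the primary and secondary endpoint analyses treat each series independently. *Treatment series* also says "The duration of active therapy following the last filled prescription or administration is set at 120 days", so a switch to a second drug inside that tail creates overlap without any intended combination. No sentence removes overlap time from a drug's denominator in analysis (c).

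The general follow-up rule is "Except for the event of interest, any of the previously mentioned cases will result in censoring". Analysis (c) makes an exception to it: for overlapping events, the event of interest itself becomes the reason for censoring.

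**The concern.** Two patients on the same pair of drugs are treated differently according to outcome. The one with an event is censored at that moment and the event is dropped. The one without an event stays at risk and keeps adding person-time. This is informative censoring in its extreme form, because during overlap it happens if and only if the event happens. All-cause mortality, a secondary outcome, shows it plainly: a patient who dies during overlap is censored at death, the death is not counted, and the time before it remains.

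At stake is how the robustness check is read. A drug that is often combined can show a lower rate under (c) purely because its overlap events have been deleted. That could be taken as evidence that the drug is safe on its own, or as a lack of robustness that is an artefact. The same applies to Cox models run under (c). AD comparators without systemic therapy have no overlapping events to lose, so hazard ratios for drugs with overlap are pulled down.

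**Working it through.** The protocol gives no figure for analysis (c), so there is none to reproduce.

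**Inputs**
- Event rule for (c): section 8.7, *Events* and *Tertiary statistical analysis*, and the Abstract.
- Overlap time kept in each drug's denominator: inferred from *Treatment series*, *Follow-up and exposure and censoring* and the endpoint analyses in section 8.7.
- Illustrative rate h = 150 per 10,000 person-years, from the 1.5% annual MACE rate in section 8.2, *Representativeness*.
- p, the share of a drug's exposed time that overlaps another drug: not given; assumed 10% to 50%.
- k, the ratio of the event rate under combined therapy to that on one drug: not given; assumed 1 to 2.
- q, the share of a drug's overlap time in which it is the longer-used drug: not given; 0, 0.5 and 1 shown.

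**Step 1: what (c) estimates.** Let E1 and T1 be events and time on one drug alone, and T2 the overlap time. Then

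rate(c) = E1/(T1 + T2) = (E1/T1) × T1/(T1 + T2) = single-drug rate × (1 − p).

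This is an identity and needs no constant hazard. k does not appear in it, so (c) carries no information on risk under combined therapy.

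**Step 2: against the full on-treatment rate.** That rate is h[(1 − p) + kp], so the ratio is (1 − p)/[(1 − p) + kp]. At k = 1 the shortfall is exactly p.

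**Step 3: against the primary rule.** At k = 1, with overlap time kept in both drugs' denominators, the primary rate is h[(1 − p) + pq] and (c) is h(1 − p). The shortfall is pq/[(1 − p) + pq]. It is zero at q = 0 and equals p at q = 1.

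| p | (c), per 10,000 PY | below full rate, k = 1 | below full rate, k = 2 | primary rate, k = 1, q = 0.5 | below primary |
|---|---|---|---|---|---|
| 10% | 135 | 10% | 18% | 142.5 | 5% |
| 20% | 120 | 20% | 33% | 135 | 11% |
| 30% | 105 | 30% | 46% | 127.5 | 18% |
| 50% | 75 | 50% | 67% | 112.5 | 33% |

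**Step 4: simulation.** 2,000,000 patients were simulated with a single-drug rate of 150 per 10,000 person-years, about 24% of time in overlap, and overlap timing unrelated to risk.

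| Rate per 10,000 PY | k = 1 | k = 2 |
|---|---|---|
| all on-treatment events | 150.1 | 186.2 |
| (c) as written | 113.7 | 113.8 |
| overlap events and time both removed | 150.0 | 149.9 |
| censored at the start of overlap | 149.5 | 150.6 |

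As written, (c) misses the single-drug rate by about the overlap share and does not change when combined therapy doubles the risk. Both alternatives recover the single-drug rate.

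**The case against.** The strongest defence is that (c) is an allocation exercise, not an estimator of single-drug risk. With denominators fixed, giving the event to both drugs and giving it to neither are the most and the fewest overlapping events a drug can receive. They bracket the other two rules, and a low value under the neither-drug option is then expected. That is a coherent use, and the fix leaves room for it. But the protocol does not call (c) a bound; it presents it as a check of robustness.

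Four stronger readings are tempting, and the documents do not support them:

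- A reader might infer that (c) must fall below the primary result for every drug with overlap. It need not. A drug that is always the later addition already receives no overlapping events under the primary rule, so (c) equals the primary result for it. If overlap time were also credited only to the longer-used drug, (c) would not be biased for the later one at all.
- A reader might take the 10% to 50% range as the gap from the primary analysis. It is the gap from the full on-treatment rate, and matches the primary gap only at q = 1.
- A reader might take retention of overlap time as stated. It is inferred. If that time were removed from the denominators, the bias would vanish.
- A reader might assume that (c) is meant to estimate the single-drug rate. The protocol states only the robustness purpose.

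It is also fair that this is one of three overlap sensitivity analyses, presented separately, in a descriptive study that tests no hypotheses.

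**Conclusion.** The point holds in limited form. As written, (c) uses outcome-triggered censoring and returns the single-drug rate multiplied by the share of time on one drug alone. The event rule is fixed consistently in three places, so this is not a detail left open; only the treatment of overlap time is inferred.

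The identity rests on that inference alone. The sizes also rest on a constant hazard and on assumed values of p, q and k: 10% to 50% below the full on-treatment rate for p of 10% to 50% at k = 1, and more if combined therapy raises risk; and from zero (q = 0) through 5% to 33% (q = 0.5) below the primary result at k = 1. Hazard ratios under (c) against comparators without systemic therapy are pulled down in the same way for drugs with overlap. The primary rates, the main comparisons and the other two overlap analyses are not affected.

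**What to change.** In the Abstract and in section 8.7 (*Events* and *Tertiary statistical analysis*), define (c) so that both events and person-time during overlap are excluded. At-risk time on either drug stops at the start of overlap, whether or not an event follows, and resumes only when a single drug is in use.

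State alongside it that this estimates the single-drug rate provided that starting or stopping a second drug is not itself related to event risk. Report overlap events and overlap person-time as a separate combined-therapy row, so that nothing is lost from view.

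If the neither-drug count is kept as well, label it a lower bound paired with (b), not a robustness estimate.

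The cost is a short text change in three places. Overlap dates already follow from the treatment series. The downside is fewer person-years in this one analysis. Because its denominator then differs from the primary one, a gap between the two reflects changed person-time as well as attribution, and the report should say so.

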## 8.8. Quality Control

Denmark provides universal healthcare coverage funded primarily through general taxation. Services are free at the point of care for all residents. The country is divided into regions and their responsibilities are defined by the Danish Health Act (Sundhedsloven). Regional authorities manage public hospitals, including staffing, budgeting, and infrastructure. Hospitals often rely on regional SOPs rather than site-specific ones. This centralized governance ensures consistency in quality management, business continuity, and regulatory compliance across institutions.

The Danish Healthcare system aligns with European and international standards, making it a reliable partner for global clinical research and pharmaceutical collaboration. Denmark maintains over 60 national health registries (Danish Registries EMA Data source ID 42187), governed by the Danish Health Data Authority (HMA-EMA catalogues: Institution ID 3331256 <https://catalogues.ema.europa.eu/institution/3331256>) and 150 socioeconomic registries. These registries are population-based, interlinkable via the Civil Registration Number (CPR), and renowned for their completeness, longitudinal depth, and high data validity. Data are anonymized or pseudonymized before use, and strict safeguards ensure confidentiality and compliance with GDPR.

Statistics Denmark is the primary source of official statistics in Denmark, covering a broad range of areas relevant to public health, including population demographics, health statistics, and economic data.

The requirement for official statistics follows on the Act on Statistics Denmark, which provides the formal framework for official statistics in Denmark (appendix 1, Statistics Denmark's Information Security Policy). In addition, the statistics must meet requirements developed in international cooperation. Official statistics must also satisfy quality requirements formulated in the European Statistics European Code of Practice, which includes transparency about methods and production routines.

Detailed technical documentation covering the primary backup infrastructure and associated fallback environments is held by Statistics Denmark and is not distributed to external institutions. External parties receive the information contained in Statistics Denmark's Information Security Policy (appendix 1), which summarises the available safeguards without exposing sensitive configuration details. All backup and recovery controls are implemented within Statistics Denmark's ISO/IEC 27001-certified information-security management system, ensuring they meet internationally recognised standards for confidentiality, integrity, and availability and the requirements from the Danish Agency for Digitisation and the Danish Centre for Cyber Security (links to the compliance with GDPR, Data Confidentiality Policy at Statistic Denmark 2024 and Statistic Denmark Information Security Policy 2025: Information security and data confidentiality - Statistics Denmark).

Statistics Denmark register (log) which data sets each employee uses and follows the directions from the Data Protection Agency. External users, e.g. research scientists, must be approved and only have access to information where civil registration numbers (CPR numbers) etc. have been replaced with serial numbers that do not allow you to identify people.

Bispebjerg Hospital is a part of the Capital Region of Denmark. It is registered in the HMA-EMA- catalogues under Institution ID3331470. Currently it is a partner in the following studies: EUPAS4072 (ongoing, non-voluntary PASS) and EUPAS34845 (ongoing, voluntary PASS). The data is retrieved specifically from specifically the National Patient Register (Landspatientregisteret) (EMA Data source ID: 1111181, Landspatientregisteret (National Patient Register) | HMA-EMA Catalogues of real-world data sources and studies) and Statistics Denmark.

In the Hospitals under the Capital Region, the safety and quality areas are governed by the overarching Unit for Quality, Research, and Patient Safety. Their tasks include, among other, responsibilities related to the national quality program, patient safety, pharmaceuticals, hygiene, clinical guidelines, quality databases, etc. They support quality work at the region's hospitals in collaboration with the region's IT organization, the clinical (specialty) councils, other administrative units, the executive management, and the political committees. A main task is to facilitate work on quality and patient safety in the region and to create a basis for decision-making that benefits the entire healthcare system. They govern work on clinical quality databases, Support the region's document management system and the development of regional and cross-regional guidelines (VIP), Support the work related to the National Quality Program, including learning and quality teams (LKT) and support patient safety efforts in relation to the Health Platform (Sundhedsplatformen).

Locally, the continued data storage, and subsequent management and analyses will be conducted according to the Department of Dermatology, Bispebjerg Hospitals standard operating procedures and in compliance with the Capital Region (Region Hovedstaden). All study documents (protocol, report, publications) will be reviewed by the primary investigator (i.e., [name] [name]). The Department of Dermatology, Bispebjerg Hospital will ensure the necessary compliance with local data protection, storage and archiving, and patient privacy laws and regulations and will obtain all permissions necessary to conduct this study.

A quality management system is in place locally to ensure the procedure for the preparation, approval, implementation, and revision of Standard Operating Procedures and guidelines within the research unit, and to ensure that the unit's other documents, e.g., worksheets for specific trials, are document-controlled and archived in accordance with national legislation in the area (appendix 2, Kvalitetssystemet, Hud-og Sårafdelingens forskningsenhed).

The Code of Conduct for Responsible Research (appendix 3) outlines the University of Copenhagen's Code of Conduct for Responsible Research, which includes clear rules and procedures for handling suspicions of research misconduct and other breaches of responsible conduct of research. It describes mechanisms which are designed to ensure that all reports of research misconduct are taken seriously and investigated thoroughly while protecting the rights and confidentiality of the individuals involved. They include 1) Direct

Reporting, 2) Research Integrity Officer, 3) Anonymous Reporting and 4) Whistleblower Protection.

## 8.9. Limitations of the Research Methods

This study is based on data from Denmark, which introduces certain limitations regarding the generalizability of the findings. The Danish population is relatively homogenous in terms of ethnicity and socioeconomic structure, which may limit the direct applicability of results to more diverse populations. Additionally, Denmark has a high standard of living and a universally tax-funded healthcare system that ensures equal access to medical care. While this provides a robust setting for epidemiological research, it may not reflect healthcare access, quality, or utilization patterns in countries with different healthcare models. These contextual differences should be considered when interpreting the results and comparing them to findings from other regions or healthcare systems.

Diagnosis, comorbidities, medical history and outcomes will be identified using the ICD-8 and -10 diagnosis codes, which might be subject to potential miscoding. However, this is partly mitigated by using dermatologist verified AD diagnosis. Based on clinical experience, outcomes of this severity are unlikely to be over- or underreported. However, the events can be misdiagnosed and improperly entered in to the registries.

Typically, prescription of a medication does not necessarily indicate that the medication was taken as prescribed. Similarly over-the-counter medications will not be captured in the databases, and the effect of these cannot be elucidated.

The investigated medications are used for multiple indications, therefore it is possible that the medications, e.g. prednisolone, was prescribed for another diagnosis than AD. However, this is attempted to be counterbalanced, as patients with concurrent diagnoses where the investigated treatments also were used, were excluded from the study.

## 8.10. Other Aspects

Not applicable.

## 9. PROTECTION OF HUMAN PARTICIPANTS

### 9.1. Patient Information

This study involves data that exist in deidentified/anonymized structured format and contain no patient personal information.

### 9.2. Patient Consent

As this study involves deidentified/anonymized structured data, which according to applicable legal requirements do not contain data subject to privacy laws, obtaining informed consent from patients by Pfizer is not required.

### 9.3. Institutional Review Board (IRB)/ Ethics Committee (EC)

According to Danish legislation ("Lov om videnskabetisk behandling af sundhedsvidenskabelige forskningsprojekter") observational studies not involving primary analysis of human tissue are exempt from ethical review (§14, section 2). In this non-interventional study ethical review is therefore not needed. No waiver was received. The study will be registered in the Capital Regions inventory, which constitutes the necessary legal approvals.

### 9.4. Ethical Conduct of the Study

The study will be conducted in accordance with legal and regulatory requirements, as well as with scientific purpose, value, and rigor and follow generally accepted research practices described in:

- Guidelines for Good Pharmacoepidemiology Practices (GPP). Public Policy Committee, International Society of Pharmacoepidemiology. Pharmacoepidemiology and Drug Safety 2015; 25:2-10.  
<https://onlinelibrary.wiley.com/doi/full/10.1002/pds.3891>
- Good Practices for Outcomes Research issued by the International Society for Pharmacoeconomics and Outcomes Research (ISPOR)  
[http://www.ispor.org/workpaper/practices\\_index.asp](http://www.ispor.org/workpaper/practices_index.asp)
- Good practices for real-world data studies of treatment and/or comparative effectiveness: Recommendations from the joint ISPOR-ISPE Special Task Force on real-world evidence in health care decision making  
<https://www.ncbi.nlm.nih.gov/pmc/articles/PMC5639372/>
- European Medicines Agency (EMA) European Network of Centres for Pharmacoepidemiology and Pharmacovigilance (ENCePP) Guide on Methodological Standards in Pharmacoepidemiology  
[http://www.encepp.eu/standards\\_and\\_guidances/methodologicalGuide.shtml](http://www.encepp.eu/standards_and_guidances/methodologicalGuide.shtml)

